11.3.3 Distant Metastasis

Clear evidence of distant metastases (lung, bone, brain, etc.); biopsy is recommended where possible. A solitary, spiculated lung mass/nodule is considered a second primary neoplasm unless proven otherwise.

11.3.4 Second Primary Neoplasm

Tumor reappearing with the initial and immediate adjoining anatomical region of the primary will be considered local recurrence. Multiple lung nodules/masses are considered distant metastases from the index cancer unless proven otherwise.

11.4 Criteria for Discontinuation of Protocol Treatment

- Progression of disease;
- Unacceptable adverse events per the judgment of the treating physician(s);
- Patient refusal.

If protocol treatment is discontinued, follow up and data collection will continue as specified in the protocol.

11.5 Quality of Life/Patient-Reported Outcomes Instruments

Note: Patients must be offered the opportunity to participate in the correlative components of the study, such as quality of life assessment. If the patient consents to participate in the quality of life (QOL) component of the study, sites are required to administer the baseline QOL and PRO assessments prior to the start of protocol treatment: the PSS-HN, FACT-HN, and XEQOLS. Outcomes will be assessed at baseline (pretreatment) and at 3, 12, and 24 months from completion of radiation treatment.

- #### **11.5.1 *The Functional Assessment of Cancer Therapy-Head & Neck (FACT-H&N)*** is a multidimensional, patient-self report quality of life (QOL) instrument specifically designed and validated for use with head and neck patients. The patient can complete the 12-item head and neck subscale in 5-10 minutes. The site research nurse or CRA is encouraged to be sensitive to each patient's demeanor. If patients appear particularly uncomfortable answering a question, they will be informed that they can skip that question. Similarly, interviewers will give patients a short break if the patient appears fatigued or otherwise in need of a few minutes break.

- 11.5.2** *The University of Michigan Xerostomia-Related Quality of Life Scale (XeQOLS)* consists of 15 items covering 4 major domains of oral health-related quality of life: physical functioning, personal/psychological functioning, social functioning, and pain/discomfort issues. The patient can respond to the 15 items in the scale in approximately 5 minutes. The Scale is only available in English.
- 11.5.3** *The Performance Status Scale for Head and Neck Cancer (PSS-HN)* consists of assessment of 3 functional areas (subscales): Normalcy of Diet, Eating in Public, and Understandability of Speech. The site research nurse or clinical research associate (CRA) will administer the PSS-HN. Interviewers are encouraged to be sensitive to each patient's demeanor. If patients appear particularly uncomfortable answering a question, they will be informed that they can skip that question. Similarly, interviewers will give patients a short break if the patient appears fatigued or otherwise in need of a few minutes break. The interviewer rates the patient on each scale based on the patient's responses to targeted questions. The PSS-HN takes approximately 5 minutes to complete.

***If a data form is available for web entry, it must be submitted electronically.**

Patients will be identified by initials only (first middle last); if there is no middle initial, a hyphen will be used (first-last). Last names with apostrophes will be identified by the first letter of the last name.

12.1 Summary of Data Submission (9/27/16)

Item	Due
Demographic Form (A5) Initial Evaluation Form (I1) Pathology Report (P1) Slides/Blocks (P2) PSS-HN (QP) FACT-HN (FA) Xe-QOL (L4)	Within 14 calendar days of study entry
Treatment Form (TF)	Within 7 calendar days of end of treatment
Pill Diary (DP)	End of concurrent treatment and every 30 calendar days during maintenance treatment
Surgery Form (S1) Surgical Operative Report (S2) Surgical Pathology Report (S5)	Only for patients who have surgery to the primary site and/or to regional nodes post-treatment
Radiotherapy Form (T1) Daily Treatment Record (T5)	Within 7 calendar days of RT end
PSS-HN (QP) FACT-HN (FA) Xe-QOL (L4)	At 3, 12, and 24 months from end of RT
Follow-up Form (F1)	q3 mos. for years 1-2, q6 mos. for years 3-5, then annually until publication of study results

12.2 Summary of Dosimetry Digital Data Submission (Submit to RTOG Headquarters; see Section 12.2.1)

Item	Due
Preliminary Dosimetry Information (DD) Digital Data Submission – Treatment Plan submitted in DICOM format to RTOG via TRIAD exported from treatment planning machine by Physicist Digital data submission includes the following: 
• DICOM CT data (non-contrast CT and CT with contrast; see Section 6.3.2)• DICOM STRUCTURE• DICOM RT PLAN• DICOM DOSE	Within 7 calendar days of start of RT

NOTE: Sites must notify RTOG via e-mail [contact] after digital data is submitted. The e-mail must include both the study, “Foundation 3501”, and case numbers.

Digital Data Submission Form (DT) - Web data entered (form is located on RTOG website: Foundation 3501 under Forms).

Final Dosimetry Information Radiotherapy Form (T1) Daily Treatment Record (T5)	Within 7 calendar days of RT end
---	----------------------------------

Modified digital patient data as required by RTOG will be submitted via TRIAD

12.2.1 Digital Data Submission to RTOG Headquarters

Digital data will be submitted to RTOG via the site’s TRIAD account.

12.2.2 Method of Plan Submission

RTOG will provide sites with the American College of Radiology Imaging Network’s image acquisition and management software, TRIAD, via electronic installation. TRIAD offers a web-based, software solution allowing institutions to submit DICOM data securely through electronic transmission. Internal to the site, TRIAD allows the site to “DICOM push” from the site’s Treatment Planning System (TPS), thus eliminating the need to burn physical media. Once the institution has transferred the RT data onto a TRIAD workstation, the software will anonymize, encrypt, and submit the DICOM RT data via secure internet to the RTOG image archive. For more information please visit the TRIAD web site at <https://triad.acr.org>.

Institutions initiate installation of TRIAD by e-mailing the name and e-mail address of the person(s) responsible at the site for submitting RT data for the trial (recommend the Physicist and/or Dosimetrist) to [contact]. The site will then receive a TRIAD greeting letter, which describes how to prepare for the installation.

TRIAD technical assistance may be requested by e-mailing [contact]. Please always include the institution name and trial number when requesting TRIAD technical assistance.

13.0 STATISTICAL CONSIDERATIONS

13.1 Primary Endpoint

13.1.1 Progression-free survival (PFS)

13.2 Secondary Endpoints

- 13.2.1 Overall survival;
- 13.2.2 Distant metastasis;
- 13.2.3 Adverse events;
- 13.2.4 Compliance with planned treatment;
- 13.2.5 Local-regional control;
- 13.2.6 Quality of life and patient-reported outcomes;
- 13.2.7 HER2 expression, amplification and heterodimerization, EGFR ligand expression, EGFR polymorphisms, hypoxia, and EMT characteristics as biomarkers of lapatinib response, sensitivity, and resistance, PFS, and metastasis.

13.3 Randomization and Stratification (10/3/13)

Patients will be randomized to 1 of 2 treatment arms. Additionally, patients will be stratified according to age (≤ 65 vs. > 65); T stage (T1-3 vs. T4); and N stage (N0-2a vs. N2b-3).

13.4 Definitions of Failure

The following table shows how each first event will be counted for progression-free survival, local-regional failure, and distant metastasis. Anything not explicitly in the table (e.g., second primary tumor) is not considered an event, and the patient will continue to be followed for failure. For overall survival, death from any cause will be considered a failure. All failure times will be measured from randomization to the date of failure, competing risk, or last follow-up.

First event	Progression-Free Survival	Local-Regional Failure	Distant Metastasis
None	Censored	Censored	Censored
Local-regional progression or recurrence	Failure	Failure	Competing risk
Distant metastasis	Failure	Competing risk	Failure
Death due to study cancer or from unknown causes	Failure	Failure	Competing risk
Death to due any other reason	Failure	Competing risk	Competing risk
Salvage surgery of primary with tumor present/unknown	Failure	Failure	Competing risk
Salvage neck dissection with tumor present/unknown, > 20 weeks from end of RT	Failure	Failure	Competing risk

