Variant EGFR 497 Arg allele and EGFR intron 1<20 CA repeats have been shown to be a prognostic biomarker of poor relapse-free survival (RFS) in HNSCC. However, its role in predicting lapatinib sensitivity is unknown in these patients. Since these polymorphisms can be readily measured from circulating WBC, we propose to evaluate these allelic variants in patients enrolled on this study, both to validate their prognostic significance as well as to determine their predictive effect of lapatinib response. The following assays will be performed:

- Assess EGFR gene polymorphism 497 arginine-to-lysine determined by PCR-RFLP using germline DNA collected from pre-treatment PBMC (Zhang 2005);
- Assess EGFR intron 1 CA repeat polymorphisms determined by PCR-RFLP using germline DNA collected from pre-treatment PBMC (Amador 2004).

1.6.5 Validation of Lysyl Oxidase (LOX) and Gli Family Zinc Finger (Gli1) as Biomarkers of Distant Metastasis

We have previously identified LOX and Gli1 as biomarkers for distant metastasis in HNSCC treated with radiation alone on RTOG 90-03 (Le 2009, Chung 2010). The role of these markers in HPV negative patients treated with chemoradiation has not been evaluated. We propose to validate the role of these biomarkers as predictors for distant metastasis by quantifying the level

of these proteins in pre-treatment tumor samples (as previously described in Le 2009 and Chung 2010).

1.6.6 Epithelial-to-Mesenchymal Transition (EMT) as a Prognostic Biomarker of Poor RFS and a Predictive Biomarker of Lapatinib Resistance

EMT is a well known process governing invasion and metastasis in epithelial cell tumors. Although several biomarkers have been suggested to reflect the EMT process, one common hallmark of EMT is increased vimentin expression in the tumor (Frederick 2007). Recently, certain microRNAs, including miR-212, miR-103 and miR-200 have been linked to the EMT process, and their expression levels have been correlated with poor outcomes (Hatakeyama 2010; Martello 2010). In this exploratory study, we proposed to measure EMT by the following 2 approaches and determine whether the levels of these EMT biomarkers correlate with poor RFS and/or lapatinib resistance in the treated patient population.

- Vimentin expression in pre-treatment tumors determined by automated quantitative analysis (AQUA) (Frederick 2007);

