2.2 Secondary Objectives

2.2.1 To evaluate if the addition of lapatinib to concurrent cisplatin and radiation in this patient population improves overall survival (OS);

2.2.2 To evaluate if the addition of lapatinib to concurrent cisplatin and radiation in this patient population improves control of distant metastasis;

2.2.3 To evaluate toxicity and tolerability between treatment arms;

2.2.4 To evaluate if the addition of lapatinib to concurrent cisplatin and radiation in this patient population improves local regional control;

2.2.5 To investigate quality of life and patient-reported outcomes between treatment arms;

2.2.6 To explore HER2 expression, amplification and heterodimerization, EGFR ligand expression, EGFR polymorphisms, hypoxia, and EMT characteristics as biomarkers of lapatinib response, sensitivity, and resistance, PFS, and metastasis.

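### Section 13.4 counts metastasis and local-regional failure only as first events, so objectives 2.2.2 and 2.2.4 would be answered by first-failure pattern; an any-time analysis should be added

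*Combined protocol and SAP*

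**What the plan says.** Section 13.4 classifies each patient once: "The following table shows how each first event will be counted for progression-free survival, local-regional failure, and distant metastasis". Two rows matter here:

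- Columns PFS, local-regional failure, distant metastasis: "Local-regional progression or recurrence Failure Failure Competing risk".
- Same columns: "Distant metastasis Failure Competing risk Failure".

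Time stops at whichever comes first: "All failure times will be measured from randomization to the date of failure, competing risk, or last follow-up". The only provision for continuing to follow a patient for failure covers events that are not in the table, such as a second primary. It does not reach local-regional failure or metastasis, which are listed.

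Section 13.6 carries this into the analysis. Both endpoints are estimated by cumulative incidence with the competing risks of Section 13.4, and the arms are compared by a cause-specific log-rank test. No sensitivity analysis counts later events.

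Objective 2.2.2 asks whether lapatinib "improves control of distant metastasis", and objective 2.2.4 asks the same of local-regional control. Neither is limited to first failure.

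Follow-up does not end at progression. Section 11.4 lists progression as a reason to stop treatment and adds: "If protocol treatment is discontinued, follow up and data collection will continue as specified in the protocol". Section 11.2.6 schedules chest CT and head-and-neck imaging to year 5.

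One further row, "Death due to study cancer or from unknown causes", is coded as a local-regional failure when it is the first event.

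**The concern.** A true competing event makes the event of interest impossible. Death does that; local-regional recurrence does not prevent a later metastasis, nor the reverse. By ending observation at either one, the plan measures where disease first failed. That is a legitimate quantity, but it is not the one the objectives name.

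Three consequences are possible. Later events drop out of comparisons that are already small. The first-event metastasis curve depends on local control: an arm with fewer local-regional failures keeps more patients at risk of a first-event metastasis, so its curve can rise with no effect on spread. And deaths from study cancer or unknown cause, with no recurrence recorded, are assigned to local-regional failure, which can blur that contrast.

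Section 1.6.5 also has an interest in metastasis as such: "We propose to validate the role of these biomarkers as predictors for distant metastasis" (LOX and Gli1). Section 13.4 holds the only definition of a metastasis event in the documents.

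**Working it through.** **The plan's own figure.** No event count, power or sample size is stated for metastasis or local-regional control. The one figure to reproduce is the 69 PFS events: HR 0.65, one-sided alpha 0.20, power 0.80, one look at half the events, Lan-DeMets O'Brien-Fleming efficacy spending and non-binding rho(1.5) futility spending. The required drift is 1.784, so events = 4 × 1.784² / (ln 0.65)² = 68.6, rounded up to 69. The boundaries 0.0699, 0.1803 and 0.5827 also reproduce. PFS is a first-event endpoint by definition, so nothing below touches this design.

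**Share of metastases not counted.** All rates here are assumptions, because the documents give no split of failures:

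- first-event hazard H = 0.30/year
- local-regional first (hazard l): 50-65% of H
- metastasis first (hazard d): 15-25% of H
- death after local-regional failure m = 0.7/year
- metastasis hazard after local-regional failure q: from unchanged (q = d) up to 0.30/year
- horizon 3 years; k = q + m

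Counted: F = (d/H)(1 − e^(−3H)).

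Not counted: U = (l·q/k) × [(1 − e^(−3H))/H − e^(−3k)(1 − e^(−3(H−k)))/(H−k)].

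| Case | l | d | q | F | U | U/(F+U) |
|---|---|---|---|---|---|---|
| Lowest | 0.150 | 0.075 | 0.075 | 14.84% | 1.93% | 11.5% |
| Highest | 0.195 | 0.045 | 0.30 | 8.90% | 8.59% | 49.1% |

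So about 12-49% go uncounted. Two cross-checks with other assumptions agree.

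- Using the control hazards in Section 13.5 (0.37 in year 1, 0.15 in year 2), with local-regional share 40-60%, metastasis share 20-30%, later metastasis 0.1-0.4/year and death 0.5/year after local failure, 10-46% are missed by 2 years.
- Of 69 first events with the same shares, and 10-30% of local-first patients later metastasising, 14-21 metastases are counted and about 3-12 are not (12-47%).

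**Effect of better local control alone on the first-event curve.** Take l = 0.18, d = 0.06, other deaths 0.06, and no effect on d:

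- HR 1 for local-regional failure: 0.06/0.300 × (1 − e^(−0.900)) = 11.9%
- HR 0.65: 0.06/0.237 × (1 − e^(−0.711)) = 12.9%
- HR 0.50: 0.06/0.210 × (1 − e^(−0.630)) = 13.4% (13.35% before rounding)

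The rise is 1.0 to 1.5 points. With 142 patients and 1:1 allocation assumed (no ratio is stated), 71 per arm × 0.010 to 0.015 is 0.7 to 1.1 patients.

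**Effect on the planned test.** In the same scenario the first-event metastasis hazard is 0.06/year in both arms, so the cause-specific log-rank test is under its null. It is not pushed towards harm; it only lacks the later events.

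**The any-time endpoint in the same scenario (F + U), for HR 1, 0.65, 0.50:**

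- q = 0.06 (unchanged): 13.7%, 14.2%, 14.4%
- q = 0.30: 19.8%, 18.4%, 17.7%

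So the two definitions can move in opposite directions, but only if local failure raises the hazard of metastasis. If it does not, both rise slightly.

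**The case against.** The strongest reply is that first-failure cumulative incidence with a cause-specific log-rank test is coherent and openly specified. It answers a recognised question and concerns secondary endpoints with no stated power or threshold; the phase III decision rests on PFS. That stands, and it limits the point to an addition.

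Several stronger readings are tempting and are not supported:

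- *The planned comparison will show a spurious trade-off between local control and metastasis.* Only the descriptive curve shifts, by about one patient per arm under the assumptions above. The planned test does not share that shift under constant independent hazards.
- *The any-time definition is the correct one and should replace Section 13.4.* It can also rise when only local control improves, because patients live longer at risk. When local failure raises the metastasis hazard, it mixes benefit through local control with any direct effect on spread. Salvage treatment can influence later events. These are two estimands with different weaknesses.
- *The later events are already on the forms.* Section 11.4 supports continued follow-up, but Section 12.1 gives only due dates for the follow-up form. Its content is not shown.
- *The LOX and Gli1 work uses the truncated endpoint.* This is plausible, since no other definition exists, but Section 1.6.5 defines no endpoint and the marker paragraph of Section 13.6 does not cite Section 13.4.
- *Only unknown-cause deaths need recoding.* Study-cancer deaths share that row, so moving one and not the other would be inconsistent. The documents give no basis for sizing the effect of either.

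What the reply does not answer is that objectives 2.2.2 and 2.2.4 carry no first-failure limit, and no planned analysis addresses them as worded.

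**Conclusion.** The mismatch between objectives and analysis is established from the text: a metastasis after local-regional failure, or the reverse, enters neither endpoint. It is not an arithmetic error. The size is not established. The 12-49% range rests wholly on assumed shares and post-failure rates, with a flat 0.30/year hazard where the plan itself gives 37% and 15% for the first two years; other assumptions give 10-46% and 12-47%. The loss is of information and of relevance to the stated question, with little distortion of the planned test. PFS, OS, the 69 events and the stopping boundaries are unaffected. This is a cheap improvement confined to secondary endpoints.

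**What to change.** 1. In Sections 13.4 and 13.6, add an analysis of distant metastasis as time from randomization to metastasis whenever it occurs, with death without metastasis as the only competing risk. Add the same for local-regional failure, with death without local-regional failure as the only competing risk.
2. Report it beside the present first-event analysis, and label the latter as pattern of first failure.
3. The any-time local-regional analysis already treats every death without a documented local-regional failure as competing. Apply the same coding to the first-event analysis as a sensitivity analysis, for study-cancer and unknown-cause deaths alike.
4. Confirm that the follow-up form records metastasis and local-regional failure after a first failure of the other kind.

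The cost is a few lines of text and additional tables, provided step 4 is satisfied; if it is not, the form needs a small change. The downside is that later events may reflect salvage treatment and be less completely recorded, which is why both versions should be shown.

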13.5 Sample Size and Patient Accrual (9/27/16)

This study will be a randomized phase II screening trial as proposed by Rubinstein, et al (2005). Based on the accrual to RTOG 0129 in this population, it is expected that the monthly accrual will be 12 patients after the first 6 months post-activation (allowing for IRB approvals). In RTOG 0129, this group of patients treated on the accelerated fractionation arm had a 2-year progression-free survival (PFS) rate of 53.5%. Hazard rates for first and second years are 37% and 15%. Based on discussions with the study chair, a 35% reduction in the hazard rate is clinically meaningful. With statistical power 0.80 and significance level 0.20 (1-sided) and one interim efficacy and futility analysis, the Lan-Demets (OF) spending function boundary for efficacy and rho family spending function with parameter of 1.5 for futility were utilized to derive a nonbinding rule. A total of 69 PFS events are required. To observe the required number of events, a sample size of 158 accrued over 1.22 years with an additional 2.6 years of follow-up (total study duration 4.3 years including 6 months for IRB approvals) is required. Allowing for up to 10% of patients to be ineligible or not evaluable, **the total original required sample size is 176.**

Following activation of the study little accrual is anticipated initially. The date at which the first patient is accrued will be used as the baseline for monitoring accrual. If the total accrual during months 18 through 24 is less than 20% of the projected total for 6 months of accrual (15 patients), then the study statistician will recommend to the RTOG DMC and the sponsor that the protocol will be discontinued. If the total accrual is between 21-49%, then the protocol will continue to accrue subjects pending approval to remain open by the RTOG DMC and the study sponsor.

Revised Sample Size and Patient Accrual

As of September 2016, the observed accrual rate in this study is about 30 patients/year (2.5/month). To finish accrual within a reasonable timeframe and to maintain the same design parameters detailed above, we plan to accrue a total of 142 patients (128 analyzable), with a total accrual duration of 4.7 years instead of 5.9 years. According to this plan, we will finish accrual around March 2017.

13.6 Analysis Plan (9/27/16)

Progression-free and overall survival rates will be estimated using the Kaplan-Meier method (1958) and rates of distant metastasis (DM) and local-regional control (LRC) by the cumulative incidence method (Kalbfleisch 1980) to account for competing risks (see Section 13.4). The distributions of the progression-free and overall survival times will be compared between treatment arms with a one sided log rank test (Mantel, 1966). Distant metastasis and local-regional control will be compared using cause-specific log rank test. If the resulting p-value for PFS is < 0.1803 , the result will be interpreted as a significant indication of lapatinib improving progression-free survival of these patients to warrant a definitive phase III trial.

Only adverse events (AEs) assessed to be definitely, probably, or possibly related (if the relationship is missing, it will be assumed to be definitely, probably, or possibly) to protocol treatment will be considered. The rates of adverse events and treatment compliance will be estimated using a binomial distribution along with their associated 95% confidence intervals and will be compared using Fisher's exact test.

Comparison of change from baseline quality of life scores between the 2 arms will be done using a 2-sample independent t test. With 158 patients, we will have 87% power to detect an effect size of 0.5 with a two-sided type I error rate of 5% and the statistical power will be 79% and 66% to detect effect sizes of 0.5 with 126 and 94 patients. Analysis of the covariance model (ANCOVA) will be used to adjust for effects from other factors.

For analysis of local-regional control, distant metastasis, PFS, and OS, we will examine whether patients with normal baseline levels of biomarkers have a different prognosis than patients with abnormal baseline levels by calculating the product-limit estimates of the survival function and comparing those estimates using the log-rank statistic. The relationship between local-regional control, distant metastasis, PFS, OS, and abnormal baseline marker levels also will be explored by fitting Cox proportional hazards regression models, both adjusted for baseline disease and patient characteristics and unadjusted. Assuming usable baseline tissue/blood samples can be obtained from 118 eligible patients (~75%), this will provide at least modest power (>69%) to detect large differences (hazard ratios > 2.0) between patients with normal and abnormal marker levels, assuming 50% abnormal prevalence, with a two-sided 5% alpha, for the PFS endpoint.

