13.6.2 Significance Testing for Early Termination and Reporting

One interim treatment comparison will be performed when 50% (34 PFS failures) of the 69 required number of PFS failures are observed. Only the primary endpoint will be tested in the interim analysis. The efficacy will be tested using boundary of 0.0699 on the p value scale for the interim tests and 0.1803 for the final analysis to preserve an overall alpha level of 0.20 for the study. A single interim futility analysis will be conducted when one-half (34) of the requisite events for definitive analysis have been observed. If the p value is equal to or greater than 0.5827 favoring the control (i.e. in the wrong direction with respect to demonstrating that the lapatinib arm is more favorable), then early stopping will be considered. The results will be reported to the RTOG DMC with the treatment blinded. The responsible statistician may recommend early reporting of the results and/or stopping accrual (if applicable) of the trial if the treatment effect with respect to PFS is highly significant or if it is not likely to be.

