13.6.4 Analysis for Reporting the Final Treatment Results

The analysis to report the definitive results of treatment will be undertaken when 69 events (total from both arms) have been reported for the primary endpoint, PFS, unless the criteria for early stopping are met. The time from when accrual is finished to this analysis is projected to be approximately 2.7 years based on the observed accrual rate. All randomized patients (ITT) will be included in this analysis. Eligible patients with both on-study and follow-up information will be considered for sensitivity analysis. The usual components of this analysis are:

- Tabulation of all cases entered, and any excluded from analysis with reasons for exclusion;
- Patient accrual rate;
- Institutional accrual;
- Distribution of important baseline prognostic variables;
- Frequency and severity of adverse events;
- Observed results with respect to the endpoints described above.

The difference in PFS between the control arm and the experimental arm will be tested using the one sided log-rank statistic at the significance level of 0.1803 given that the one interim analysis is carried out and shows no statistical significance. If the resulting p-value for efficacy is <0.1803, this result will be interpreted as an indication of lapatinib in improving progression-free survival in these patients.

A final analysis report will be prepared and provided for review by the co-investigators. Results for dissemination will be developed, and a manuscript drafted for review, approval, and submission. After manuscript acceptance, patient follow up will be discontinued and the trial terminated. It is anticipated that termination will occur approximately 3.9 years from when the accrual is finished. This time-frame may be extended depending on factors such as the observed accrual and event rates, in which case a new trial termination date will be established.

REFERENCES

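### Optional low-cost improvement, not an error: randomisation is stratified by age, T stage and N stage, but the PFS and OS tests do not use these factors; adjusting would change PFS power by about 0 to +3 points

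*Combined protocol and SAP*

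**What the plan says.** - Section 13.3: "patients will be stratified according to age" (65 or under against over 65), T stage (T1-3 against T4) and N stage (N0-2a against N2b-3). All three are recorded on the Step 1 eligibility checklist.
- Section 13.6: PFS and OS "will be compared between treatment arms with a one sided log rank test".
- Section 13.6.4: the final PFS difference is "tested using the one sided log-rank statistic at the significance level of 0.1803". The section attaches a condition to that threshold: "given that the one interim analysis is carried out and shows no statistical significance". The only sensitivity analysis named there changes the patients analysed, not the model.
- Section 13.6.2: one look at 34 of 69 PFS events, with efficacy boundaries 0.0699 and 0.1803 "to preserve an overall alpha level of 0.20 for the study" and futility at p of 0.5827 or more.
- Baseline adjustment appears only elsewhere in 13.6: ANCOVA for quality of life, and Cox models for biomarkers, "both adjusted for baseline disease and patient characteristics and unadjusted".

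No section adjusts the PFS or OS treatment comparison, and none names a treatment hazard ratio as an estimate.

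**The concern.** Stratified allocation balances the arms on factors expected to matter. An unadjusted log-rank test does not use that balance. Its variance still allows for chance imbalance that the design has largely removed, so its true level falls below nominal when the factors are prognostic. In a 69-event screening trial that accepts a one-sided 0.20 in order to gain power, unused type I error is lost power in the decision whether to proceed to phase III. The three factors are already collected, so using them needs no new data.

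**Working it through.** **1. The plan's own figures.** Inputs from 13.5 and 13.6.2: one-sided level 0.20, power 0.80, hazard ratio 0.65, looks at 34 and 69 events.
- Fixed design: D = 4(z + z)² / (ln HR)² = 4(0.8416 + 0.8416)² / (0.4308)² = 11.33 / 0.1856 = 61.1, so 62 events.
- Interim efficacy by O'Brien-Fleming-type spending at half information: 2[1 − Φ(1.2816/√0.5)] = 2[1 − Φ(1.8124)] = 0.0699, as stated.
- Bivariate normal calculation with rho = 1.5 futility: final threshold 0.1803, overall level 0.2000, power 0.801 at 69 events with futility stopping (0.820 without). Futility comes out at 0.581 against the stated 0.5827.

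The events, boundaries and power reproduce.

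**2. Simulation inputs.**
- From the documents: 142 patients, 4.7 years of accrual (taken as uniform), both looks and all three thresholds. Control PFS is 0.63 at one year and 0.63 × 0.85 = 0.5355 at two, from the 37% and 15% in 13.5, which matches the stated 53.5%.
- Assumed, not in the documents: T4 40%, N2b-3 60%, age over 65 25%; 1:1 allocation in blocks of 4 within the 8 strata; the factor hazard ratios below.
- 30,000 trials per cell, Monte Carlo standard error about 0.0023.

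**3. Results.** Level is without futility stopping. Power is at a hazard ratio of 0.65 conditional on the factors, with futility followed. The adjusted test is a Cox score test with re-randomisation p-values at the unchanged thresholds.

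| Factor HRs (T/N/age) | Log-rank level | Adjusted level | Log-rank power | Adjusted power | Change (points) |
|---|---|---|---|---|---|
| 1/1/1 | 0.2005 | 0.200 | 0.796 | 0.793 | −0.3 |
| 1.5/1.5/1.3 | 0.194 | 0.199 | 0.788 | 0.792 | +0.4 |
| 2/2/1.3 | 0.187 | 0.201 | 0.776 | 0.792 | +1.7 (unrounded) |
| 2.5/2/1.5 | 0.181 | 0.200 | 0.7635 | 0.7905 | +2.7 |

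The adjusted test crosses at the interim with probability 0.068 to 0.070 under the null, against the planned 0.0699.

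**4. Like for like.** With both tests calibrated to 0.20, the differences in the same four settings are −0.3, +0.1, +0.5 and +0.9 points.

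**5. If 0.65 is the marginal hazard ratio.** In the three prognostic settings (conditional hazard ratios 0.644, 0.630, 0.619), log-rank power is 0.804, 0.815, 0.823 and adjusted power 0.808, 0.831, 0.847: +0.4, about +1.5 and +2.4 points.

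**6. Sensitivity.** With prevalences 30/40/60% (age/T/N), a Cox Wald test calibrated to 0.20 and futility followed, the change from the planned log-rank is −0.2 points (no effect), +0.5 (HR 1.5 each), +2.6 (HR 2 each) and +5.1 (HR 2.5 each, an extreme case). With 128 patients, HR 1.5 each gives +1.0. At HR 2 each, with both tests calibrated, the difference runs from +0.7 to +1.7 across 142 or 128 patients and prevalences of 50%. At HR 2 each under simple randomisation the log-rank level is 0.2023, so the conservatism comes from the stratified allocation.

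**7. Two alternatives that do worse.**
- Cox Wald at unchanged thresholds: overall level 0.204 to 0.2075. Lowering only the final threshold to 0.170 brings the overall level to 0.196 to 0.199, but the interim crossing stays at 0.073 to 0.077 against 0.0699.
- Log-rank stratified on all 8 cells: 69/8 = 8.6 events per cell on average; power 0.784 against 0.797 with no effect and 0.779 against 0.788 at 1.5/1.5/1.3.

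**8. Has the look been made?** Section 13.5 plans 142 patients "with a total accrual duration of 4.7 years instead of 5.9 years" and says "we will finish accrual around March 2017", which puts the start at about mid-2012. The simulated 34th event has its median 3.0 to 3.3 years after the start with uniform accrual, and 3.9 to 4.2 years with an assumed linear ramp. Section 7.9 carries the date 3/22/17, about 4.7 years after that start. The probability that the 34th event falls before 4.7 years is 1.00 (uniform) and 0.98 to above 0.99 (ramp).

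**The case against.** The case for leaving the plan alone is strong, and most of it stands.

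- The test is valid, and a level below 0.20 does not breach 13.6.2. This stands. A reader might infer that ignoring the strata invalidates the analysis; nothing in the documents or the simulation supports that.
- The trial was sized from unadjusted PFS rates, so 0.65 is naturally read as a marginal effect, and on that reading the log-rank keeps about 0.80 power throughout. This stands. A reader might infer from the 0.7635 above that the trial is underpowered. That figure needs both strong factors and a conditional reading of 0.65, and the documents establish neither.
- Most of the gain is recovered type I error, and it rests on assumed factor strengths in a population already restricted to selected stage III-IV disease. This stands, and limits the claim.
- The interim look has probably passed. This is likely, but reaching 34 events does not prove that the look was made, and 13.6.2 still describes it as to come.
- OS was not simulated. This stands, and no OS gain is claimed.

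What remains is modest. The trial randomises by three factors, records them, and leaves them out of the comparison that decides on phase III. The design effect is a hazard reduction, yet no treatment hazard ratio is specified.

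**Conclusion.** This is an optional refinement of a valid analysis. Held to 0.20 overall, adjustment changes PFS power by about 0 points for weak or moderate factors and about +2 to +3 for strong ones, and loses a fraction of a point if the factors are not prognostic. With both tests calibrated the difference is at most about 1 to 2 points, apart from the extreme setting of HR 2.5 for all three factors. These sizes depend on prognostic strengths, prevalences, a 1:1 ratio and a block structure that the documents do not give. If the interim look has already used the log-rank, as is likely, the primary test gains nothing, and the benefit is a pre-specified adjusted estimate that prevents later choice of covariates.

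**What to change.** The sponsor should state whether the 34-event look has been made.

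**If it has not,** pre-specify in 13.6, 13.6.2 and 13.6.4: the PFS test at both looks is a one-sided score test of treatment in a Cox model with age, T stage and N stage (as categorised in 13.3) as main effects. Its p-value comes from re-randomising treatment under the trial's own allocation algorithm and is compared with the existing 0.0699, 0.5827 and 0.1803. The unadjusted log-rank is a sensitivity analysis. If a model-based p-value is preferred, calibrate both looks; do not keep 0.0699 and lower only the final threshold. Do not use the 8-cell stratified log-rank.

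**If it has been made with the log-rank,** keep the log-rank and its boundaries as primary, and pre-specify the adjusted Cox test and hazard ratio as a sensitivity analysis before unblinding.

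**For OS,** report the same adjusted model as supportive in either case.

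**Cost:** no new data, but a protocol amendment with the site approvals that 5.1 requires. Re-randomisation needs the actual allocation algorithm, which 13.3 does not describe. The adjusted hazard ratio is conditional on the three factors and should be labelled so. If the factors are not prognostic, the re-randomisation version loses about 0.3 points of power.
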